## **J. Statistical Methods**

**1. Power Analysis.** The primary goal of this Phase II study is to demonstrate sufficient superiority of rizatriptan over placebo in the main outcome measure, 1a(1), to warrant a future Phase III trial. In the previous triptan study for VM (see Prior Controlled Study of Triptans for VM), the response rate for active drug was 3/8 (38%) versus 2/9 (22%) for placebo. If the small sample from that failed trial reflected a true response, then the odds ratio favoring the triptan for VM would be 2.1. To improve our estimate, we examined the results of two large registration trials that used a simple randomization design similar to the present proposal to test rizatriptan for conventional migraine. Those studies had response rates of 74% and 77% for rizatriptan versus 28% and 37% for placebo giving odds ratios of 7.4 and 5.7 favoring rizatriptan. The lower response rates in the VM trial most likely reflected the inadequate sample size, but could suggest that triptans are less effective for VM than conventional migraine. To account for this possibility, we took the limited results of Neuhauser, et al. as a worst-case scenario for our sample size calculation. Focusing on the main outcome measure, 1a(1), in this double-blind, randomized trial, with PASS simple randomization design and using a type I error of 0.05, type II error of 0.2 (equivalent to power of 80%), two-sided tests, then treating 120 subjects (with 2:1 ratio for treatment and placebo) will allow us to detect an odds ratio as small as 3.2. Thus, the plan to enroll 200 subjects in the Observation Phase and select 120 for the Treatment Phase will be sufficient, even if the response of VM to rizatriptan proves to be only half that of conventional migraine. Phase II trials typically gather data on secondary outcomes (e.g., 1a(2)-1d(2)) and other variables (2a-c) to inform the design of Phase III trials, but sample sizes need not be planned to demonstrate significant differences in these variables.

**2. Randomization.** A randomization scheme will be developed to assign the 120 patients expected to be included in the Treatment Phase to parallel treatment arms in a 2:1 ratio of active drug:placebo.

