
## **M. Plans to Address Limitations**

The patient flow just reviewed suggests that we will be able to meet study recruitment and retention targets. However, we intend to examine rates of enrollment into the Observation Phase and randomization into the Treatment Phase every quarter. If we fall short of targets for enrollment or randomization at any point, we will take three steps, as needed. (1) Contact patients with VM who were previously examined at our institutions. Both centers maintain databases of patients who participated in previous diagnostic studies (N>400), many of whom expressed interest in treatment trials. (2) The Mayo Clinic site will expand recruitment to the Mayo Clinic Health System of hospitals and clinics across a three-state area of the upper Midwest, and UCLA will expand recruitment to affiliated hospitals and clinics across Southern California. (3) Both sites will advertise selectively to regional and local professional organizations, patient advocacy groups, and the general public.

A negative treatment result (i.e., finding that rizatriptan is not superior to placebo) will not be a study failure. Rather, it will be evidence that rizatriptan lacks the efficacy needed to pursue a Phase III trial in patients with VM. A negative result will prompt a search for other abortive and prophylactic therapies for VM and might nudge researchers to re-evaluate the concept of VM as a migrainous phenomenon. Data collected for Specific Aim #2 should be helpful in considering alternative medications and different potential pathophysiologic processes for VM regardless of the efficacy of rizatriptan.

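### The assurance that 120 subjects suffice even at half the conventional-migraine response leaves the scale of half undefined and fails on most readings

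*Combined protocol and SAP*

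**What the plan says.** Section III.J.1 sets the design parameters as "using a type I error of 0.05, type II error of 0.2 (equivalent to power of 80%), two-sided tests" and states that "treating 120 subjects (with 2:1 ratio for treatment and placebo) will allow us to detect an odds ratio as small as 3.2". It draws on two sources. For the earlier zolmitriptan trial in vestibular migraine (VM), "the response rate for active drug was 3/8 (38%) versus 2/9 (22%) for placebo", so that "the odds ratio favoring the triptan for VM would be 2.1". For the two rizatriptan registration trials in conventional migraine it reports "response rates of 74% and 77% for rizatriptan versus 28% and 37% for placebo giving odds ratios of 7.4 and 5.7 favoring rizatriptan".

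From the detectable odds ratio it then infers that the planned sample will be enough "even if the response of VM to rizatriptan proves to be only half that of conventional migraine". It does not say whether the thing halved is the response rate, the difference from placebo or the odds ratio. It also does not name the placebo rate behind the 3.2.

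Section III.M says of a negative result that "it will be evidence that rizatriptan lacks the efficacy needed to pursue a Phase III trial in patients with VM".

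**The concern.** The sentence is the power section's conclusion on sufficiency, and it promises a specific property: 80% power against an effect half the size seen in migraine. The property depends on the scale. Halving an odds ratio is not the same as halving a response rate or halving a benefit over placebo. Even on the odds-ratio scale, half of 5.7 is below the stated 3.2.

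What is at stake is how a null result is read. Someone who takes the assurance together with section III.M would conclude that a non-significant trial had tested a half-size effect with 80% power and found against it. If power at that effect is nearer 55-70%, the trial would miss it about 30-45% of the time rather than 20%.

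**Working it through.** **Inputs.** 80 rizatriptan and 40 placebo subjects (120 at 2:1), two-sided 0.05, target power 80%; migraine rates 74% vs 28% and 77% vs 37%, with odds ratios 7.4 and 5.7; prior VM placebo rate 22%. All are from section III.J.1. The placebo rate behind the 3.2 is not given, so 22% is an assumption, and 28% and 37% are also used to show the range. One binary outcome per subject, as in that section.

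**Formula.** With placebo rate p0, active rate p1, n0 = 40, n1 = 80 and pooled rate p = (40·p0 + 80·p1)/120:

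- SE0 = √[p(1−p)(1/40 + 1/80)]
- SE1 = √[p0(1−p0)/40 + p1(1−p1)/80]
- power = Φ[(|p1 − p0| − 1.96·SE0)/SE1]
- an odds ratio OR gives p1 = p0·OR/(1 − p0 + p0·OR)

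**Step 1: reproduce the plan's figure.** At p0 = 22% and OR 3.2, p1 = 0.704/1.484 = 47.4%. Then p = 0.390, SE0 = 0.0944, SE1 = 0.0861, and power = Φ[(0.2544 − 0.1851)/0.0861] = Φ(0.805) = 79%. Power of exactly 80% needs OR 3.24 (47.8% vs 22%, 26 points). At 37% placebo it needs OR 2.99 (63.7% vs 37%, 27 points). The stated 3.2 is therefore sound.

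**Step 2: halve the odds ratio.** 7.4/2 = 3.7; 5.7/2 = 2.85; mean (7.4 + 5.7)/2 = 6.55, and half of that is 3.28.

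| Halved OR | Placebo | Active | Power |
|---|---|---|---|
| 3.7 | 28% | 59.0% | 91% |
| 3.7 | 22% | 51.1% | 89% |
| 3.28 (mean) | 32.5% | 61.2% | 86% |
| 3.28 (mean) | 22% | 48.0% | 81% |
| 2.85 | 37% | 62.6% | 76% |
| 2.85 | 22% | 44.6% | 69% |

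**Step 3: halve the absolute benefit.** (74 − 28)/2 = 23 points; (77 − 37)/2 = 20 points.

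| Placebo | Active | OR | Power |
|---|---|---|---|
| 28% | 51% | 2.68 | 68% |
| 37% | 57% | 2.26 | 54% |
| 22% | 45% | 2.90 | 71% |
| 22% | 42% | 2.57 | 59% |

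First row in full: p = 0.433, SE0 = 0.0960, SE1 = 0.0904, power = Φ[(0.23 − 0.188)/0.0904] = Φ(0.464) = 68%.

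**Step 4: halve the response rate.** 74/2 = 37% and 77/2 = 38.5%. Against the 22% VM placebo rate, power is 37.5% (OR 2.08) and 43.7% (OR 2.22).

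Exact enumeration of the chi-square test agrees with these powers to within about one percentage point.

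**Step 5: sensitivity to repeated attacks.** Suppose every subject treats three attacks, with a within-subject correlation of 0.3 to 0.7 (assumed; the documents give none). The design effect is 1 + 2 × correlation, so the effective placebo count is 120/1.6 = 75 down to 120/2.4 = 50. Power becomes 78-92% for 51% vs 28%, 64-81% for 57% vs 37%, and 85-96% for OR 2.85 at 37% placebo. At 37-38.5% vs 22% it is 46-71%.

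**The case against.** The best defence is that section III.J.1 argues in odds ratios throughout and the sentence follows directly from the 3.2. Half the mean migraine odds ratio is 3.28, just above 3.2, so the authors probably meant that, and on that reading the statement is true. This stands as an account of where the sentence came from, and it is why one cannot say that the design lacks 80% power at half the migraine effect on every reading. It does not rescue the sentence as written: no averaging is mentioned, a reader will not take a halved response to mean a halved odds ratio, and one of the two cited trials fails on that scale too.

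A second defence is that the main outcome in section III (Approach), 1a(1), is a proportion of treated attacks, with up to three per subject and mixed models planned in section III.J.3. That could lift power at half the benefit to or above 80% in some cases. The point has force, but the gain rests on an unstated correlation and on every subject treating three attacks. Section III.D.4 lets subjects finish with fewer, and section III.J.3 includes anyone who treats at least one. The power section counts subjects and claims no such gain. In the other direction, section III.L cites 100 treated subjects as the worst case. At that number, power at half the benefit is 47-62%.

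A third is that section III.M speaks of the efficacy needed for a Phase III trial, which is a go/no-go judgement and not a claim of no effect. That is correct, and it limits the remedy there to wording.

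A reader might go further and infer that power at half the migraine response could be as low as about 5%. That comes from setting a halved 38.5% against the 37% migraine placebo rate, which leaves a benefit of 1.5 points. It describes a drug with almost no effect, which is not a fair reading of the sentence.

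**Conclusion.** The sentence claims a property the design does not reliably have. On the section's own one-outcome-per-subject basis, power at half the migraine response is:

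- 69-91% on the odds-ratio scale, reaching 80% for half of 7.4 and half the mean but not for half of 5.7;
- 54-71% on the absolute-benefit scale, below 80% for both trials;
- about 37-44% with the response rate halved against 22% placebo.

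The failure for 5.7 needs no assumption about the placebo rate if the plan's 3.2 is accepted, since 2.85 is below it. The power percentages do rest on placebo rates of 22-37% and on one outcome per subject, and repeated attacks could raise them by an unknown amount. The 3.2 itself is not in error, and the documents do not show that 120 subjects are too few. What needs correcting is the assurance and the reading of a negative result that leans on it.

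**What to change.** In section III.J.1, delete the half-response assurance, or name the scale and restate it for each reference trial. Give the detectable effect with its assumed placebo rate: 80% power for about 48% vs 22% (OR 3.2) to 64% vs 37% (OR 3.0), a difference of about 26-27 points. Add that power at half the migraine absolute benefit is about 54-71% with one outcome per subject. If credit is to be taken for repeated attacks, state the assumed number per subject and the correlation, and show the range.

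In section III.M, say that a non-significant result is evidence against effects of about the detectable size and does not rule out a half-size effect.

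The cost is a few sentences, and a stated sensitivity that looks less favourable. The design, the sample size and the tests stay as they are.

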## III. APPROACH

We propose a two-center, randomized, double blind, placebo-controlled, parallel, three-episode, clinical trial of rizatriptan 10 mg oral tablets versus placebo for treating spontaneous vestibular attacks in patients with VM.

Our primary Specific Aim is to test hypotheses 1a-1d that rizatriptan will be:

- 1a. Superior to placebo in reducing the severity and duration of vestibular attacks as measured by:
  - (1) Proportion of treated attacks in which subjects experience a reduction in severity rating from Grade 3/2 to Grade 1/0 at one hour after taking study medication (see below for rating description). This is the main outcome measure; 1a(2)-1d(2) are secondary outcome measures.
  - (2) Proportion of treated attacks in which subjects achieve sustained relief (i.e., vestibular symptom severity rating of Grade 1/0) for 24 hours after taking study medication, without use of non-study therapies.
  - (3) Proportion of treated attacks in which subjects experience freedom from vestibular symptoms (i.e., severity rating of Grade 0) at one hour after taking study medication.
  - (4) Use of fewer non-study therapies after each attack treated with study medication.
- 1b. Superior to placebo in reducing severity of symptoms associated with vestibular attacks as measured by:
  - (1) Proportion of treated attacks in which subjects experience relief (reduction to Grade 1/0) from VM-associated symptoms (e.g., nausea, vomiting, motion sensitivity, gait disturbance, headache, photophobia, and phonophobia) at one hour after taking study medication.
  - (2) Proportion of treated attacks in which subjects achieve sustained relief from VM-associated symptoms for 24 hours after taking study medication without use of non-study therapies.
- 1c. Superior to placebo on treatment satisfaction and health-related quality of life as measured by:
  - (1) Scores on the Treatment Satisfaction Questionnaire for Medication (TSQM) at 48 hours after each attack treated with study medication
  - (2) Scores on the Short Form 12 (SF-12) at 48 hours after each attack treated with study medication
- 1d. Tolerated as well as placebo by patients with VM as measured by:
  - (1) No greater rate of treatment-emergent serious adverse events reported on the NCI Common Toxicity Criteria Scale 4.0^59 obtained 48 hours after each attack treated with study medication.

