**4. Treatment Phase.** Subjects who qualify for randomization will enter the Treatment Phase. They will be randomly assigned to parallel study arms in a 2:1 ratio of rizatriptan 10 mg encapsulated tablets or look-alike placebo capsules. Subjects will treat three vestibular attacks that manifest with Grade 3/2 vestibular symptoms. Associated symptoms, including headache, need not be present and may be of lesser severity. Headaches without vestibular symptoms are not eligible for study treatment, but may be treated in the subjects' usual manner. Subjects will be instructed to ingest one study capsule as soon as possible after onset of Grade 3/2 vestibular symptoms. They will record treatment response in their Vestibular Symptom Diaries by rating the severity of vestibular and associated symptoms at the time they take study medication and at 0.5, 1, 2, 4, 24, and 48 hours post-dose. Subjects will record adverse effects in accordance with the Common Toxicity Criteria Scale 4.0, treatment satisfaction on the TSQM, and quality of life on the SF-12 at 48 hours post-dose. Then they will contact study personnel by phone to review the attack and treatment response.

Subjects will treat one attack with study medication in a 48-hour period. Repeat dosing of study medication within 48 hours will not be permitted. Subjects must have a vertigo-free period of at least 48 hours before treating a subsequent vestibular attack with study medication. The relatively short plasma half-life of rizatriptan (2-2.5 hours) justifies the 48-hour wash out period. Subjects may use other medications to treat residual symptoms (see Concomitant Medications) but must wait at least 1 hour after taking the study medication. Additional treatments will be reported to study personnel together with other attack data. Subjects will remain in the Treatment Phase until they have treated three separate vestibular attacks, experience serious or intolerable adverse effects, withdraw for other reasons, or reach the end of the study. Study personnel will conduct telephone assessments on a monthly basis as they did during the Observation Phase. Extra visits to study clinics will be arranged as needed to re-evaluate subjects' health and treat problematic symptoms.

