**3. Statistical Analysis and Modeling.** We will use SAS and R^70 statistical software, creating ad hoc algorithms and macro procedures to solve analytical questions for which no marketed algorithms exist.

1. As a first step to understanding the nature of our data, we will conduct univariate analysis of demographics, primary and secondary outcome measures, illness-related variables (e.g., frequency, severity, and duration of vertigo attacks), associated symptoms, comorbid conditions, and self-report rating scales. The marginal distribution of each measure will be calculated at each time point and across time. The time trends of outcome measures will be evaluated by graphical analyses. For example, parallel plots for each of the outcome measures will be created to examine the patterns of change over time.

2. We will test the four hypotheses of Specific Aim #1 using bivariate methods and multivariate modeling. First, we will analyze differences between rizatriptan and placebo on all outcome measures at each time point using chi-squares to cross-tabulate categorical variables, and t-tests, analyses of variance (ANOVAs), or marginal regressions to compare continuous variables.

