3. After testing bivariate differences, we will use repeated measures mixed effects models to compare outcome measures between rizatriptan and placebo over time, and examine the effects of covariates on treatment response. As an example, for the special case of binary outcome vertigo severity (Grade 3/2 versus Grade 1/0) and the more general case of ordinal outcome vertigo severity (Grade 3, 2, 1, 0), we will use SAS PROC GLIMMIX to model the logits of cumulative probabilities including vectors for study drug, illness related variables, associated symptoms, rating scales, random effects, and time. The estimates on the linear scale will represent log cumulative odds. The cumulative logits are formed as  $\log \{ \Pr(Y_i \leq j) / \Pr(Y_i > j) \} = X_i \alpha + Z_i \gamma_i + \varepsilon_i$  for  $i=1, \dots, n$ , where  $Y_i$  is the  $n_i \times 1$  vector of the outcome measure for the  $i^{\text{th}}$  patient,  $j=0,1,2,3$ ,  $n_i$  is the number of measurements for the  $i^{\text{th}}$  subject in the period,  $X_i$  is  $n_i \times p$  known predictors (indicator signifying rizatriptan and placebo, and time variable.) The fixed effects parameter vector of  $\alpha$  is  $p \times 1$ .  $Z_i$  is  $n_i \times k$  known predictors, which are associated with the random part of the model, including time-varying and time factors.  $\gamma_i$  is the  $k \times 1$  random effect parameter vector and  $\gamma_i \sim N(0, D)$ ,  $\varepsilon_i$  is  $n_i \times 1$  and  $\varepsilon_i \sim N(0, \sigma^2 I)$ , which is independent of  $\gamma_i$ . Let

$\Sigma_i(\theta) = Z_i D Z_i^T + \sigma^2 I$  with  $\theta$  being the parameter of covariance vector. Integrating out  $\gamma_i$  in the above random effect model, we can write  $Y_i \sim N(X_i \alpha, \Sigma_i(\theta))$ .

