4. We will use this 3-step analysis procedure to test all outcome measures for hypotheses 1a-1d. However, the principal result of the study will be determined by the findings of bivariate analyses and multivariate modeling of the main outcome measure, 1.a.(1), plus favorable findings on tolerability measures, 1d(1)-1d(2). We will include all subjects who treat at least one vertigo attack with study drug (i.e., intent-to-treat analysis). A statistically significant result favoring rizatriptan over placebo on 1a(1) and absence of statistically significant differences on 1d(1)-1d(2) will support development of a Phase III clinical trial of rizatriptan for treating vestibular attacks in patients with VM. The design of future trials will also be informed by results of tests of secondary measures 1a(2)-1c(2). We did not hypothesize equal tolerability for rizatriptan and placebo, but rather an absence of significantly higher rates of serious adverse effects and drug-related treatment discontinuation, so our statistical analyses of measures 1d(1)-1d(2) will not include equivalence tests.

[figure not shown]

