7. Interim analysis: We will conduct an interim analysis at study midpoint without breaking the blind to assess (1) recruitment, (2) safety, and (3) efficacy. Plans for shortfalls in recruitment are noted below. We will terminate the study for insufficient safety if there is a statistically significant difference between arms in adverse events of greater than minor severity, or for lack of efficacy if response rates are <25% in both arms, i.e., no better than placebo rates in previous triptan trials. We will continue the study if the primary outcome, 1(a)1, is >25% in at least one arm, but not statistically different between arms. If the primary outcome is statistically different, then we will terminate the study because the primary aim will be met. We will break the blind and identify the results as positive (rizatriptan superior to placebo) or negative (rizatriptan inferior to placebo).

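### The main outcome counts attacks, but one of the two analyses that decide the trial is a chi-square that ignores clustering by subject, and no rule says which analysis prevails

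*Combined protocol and SAP*

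**What the plan says.** All references are to the combined protocol and SAP.

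- **Outcome.** Section III, 1a(1), defines the main outcome as "Proportion of treated attacks in which subjects experience a reduction in severity rating from Grade 3/2 to Grade 1/0 at one hour". The unit is the attack.
- **Attacks per subject.** Section III.D.4 randomises subjects to parallel arms and states "Subjects will treat three vestibular attacks that manifest with Grade 3/2 vestibular symptoms". All attacks of one subject therefore fall in the same arm.
- **Sizing.** Section III.J.1 states that "treating 120 subjects (with 2:1 ratio for treatment and placebo) will allow us to detect an odds ratio as small as 3.2", at two-sided 0.05 and 80% power.
- **First analysis.** Section III.J.3, item 2, will "analyze differences between rizatriptan and placebo on all outcome measures at each time point using chi-squares to cross-tabulate categorical variables". It mentions no adjustment for repeated attacks. Marginal regressions are listed there for continuous variables only.
- **Second analysis.** Item 3 fits mixed models with patient random effects. Its worked example uses the same split of Grade 3/2 against Grade 1/0. The model is described as "including vectors for study drug, illness related variables, associated symptoms, rating scales, random effects, and time", and its equation adds a normal error term to the cumulative logits.
- **Decision.** Item 4 says "the principal result of the study will be determined by the findings of bivariate analyses and multivariate modeling of the main outcome measure", and then asks for a significant result on 1a(1) without naming the test.
- **Interim.** Item 7 says "If the primary outcome is statistically different, then we will terminate the study because the primary aim will be met", again without naming a test.

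**The concern.** Attacks from the same person tend to resemble one another. A chi-square on pooled attacks ignores this, understates the standard error of the treatment difference and rejects a true null too often. The plan does contain an analysis that allows for clustering, so the clustering has not been overlooked. The difficulty is that an analysis without valid error control shares the decision with one that has it, and nothing says what happens when they disagree.

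Two decisions depend on this: whether the result supports a Phase III trial (item 4), and whether the trial stops at the interim analysis because the aim is met (item 7). If both tests must be significant, the false-positive rate stays near 0.05. If the chi-square alone can suffice, it is higher. The text fits either reading.

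**Working it through.** **1. Reproduce the plan's own figure.** Inputs from section III.J.1: 80 and 40 subjects, placebo response 22%, two-sided 0.05, 80% power. An odds ratio of 3.2 implies a response on drug of 3.2 × 0.22 / (0.78 + 3.2 × 0.22) = 0.704 / 1.484 = 47.4%. The two-proportion formula (pooled variance under the null, no continuity correction) gives 79.0% power, and 80% power at an odds ratio of 3.24. This matches the stated 3.2, so the trial was sized as if each subject gave one observation. A pooled attack-level chi-square would count up to 120 × 3 = 360.

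**2. Alpha of the pooled chi-square, by formula.** With m attacks per subject and intraclass correlation ICC, the design effect is DE = 1 + (m − 1) × ICC, and the true two-sided alpha is 2 × [1 − Φ(1.96 / √DE)]. The documents give no ICC, so 0.1, 0.3 and 0.5 are assumed. The second value of m is 245 analysed attacks / 114 randomised subjects = 2.15, from the appended Methods and Results.

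| m | ICC | DE | true alpha |
|---|---|---|---|
| 3 | 0.1 | 1.20 | 0.074 |
| 3 | 0.3 | 1.60 | 0.121 |
| 3 | 0.5 | 2.00 | 0.166 |
| 2.15 | 0.1 | 1.11 | 0.063 |
| 2.15 | 0.3 | 1.34 | 0.091 |
| 2.15 | 0.5 | 1.57 | 0.118 |

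**3. Both analyses by simulation under the null.** Beta-binomial data, 10,000 trials per cell, Monte Carlo standard error up to 0.004. The response rate of 0.40 is assumed. The chi-square has no continuity correction. The random-intercept logistic model is fitted by 15-point Gauss-Hermite quadrature and tested by likelihood ratio. Entries are for ICC 0.1 / 0.3 / 0.5.

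| | 80 vs 40 subjects, 3 attacks each | 76 vs 38 subjects, 1, 2 or 3 attacks (25/35/40%, assumed; mean 2.15) |
|---|---|---|
| chi-square | 0.076 / 0.128 / 0.163 | 0.066 / 0.095 / 0.132 |
| random-intercept model | 0.052 / 0.056 / 0.051 | 0.052 / 0.050 / 0.051 |
| both significant | 0.052 / 0.056 / 0.051 | 0.052 / 0.050 / 0.049 |
| chi-square significant, model not | 0.023 / 0.072 / 0.112 | 0.014 / 0.045 / 0.083 |

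The null response rate matters little. With three attacks each, the chi-square's alpha is 0.072 / 0.122 / 0.163 at a 25% rate and 0.070 / 0.119 / 0.162 at 50%.

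**4. Effect on the reported counts.** An uncorrected chi-square on the attack counts in the appended Results gives the naive p below. The last column divides z by √DE for ICC 0.1 to 0.5, with m = 245/114 at 1 hour and (149 + 88)/114 = 237/114 = 2.08 at 24 hours.

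| Comparison | z | naive p | p with DE |
|---|---|---|---|
| Vertigo, 1 hour: 73/153 vs 53/92 | 1.50 | 0.133 | 0.155 to 0.232 |
| Unsteadiness/dizziness, 1 hour: 29/153 vs 11/92 | 1.44 | 0.151 | 0.174 to 0.253 |
| Unsteadiness/dizziness, 24 hours: 120/149 vs 52/88 | 3.58 | 0.00035 | 0.0007 to 0.0040 |

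None of the three crosses 0.05.

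**5. Cost in power.** At an odds ratio of 3.2 (22% vs 47.4%) with one to three attacks per subject and 1,500 trials per cell, the chi-square has power 0.966 / 0.957 / 0.935 and the model 0.957 / 0.928 / 0.893. With three attacks each, the model has 0.992 / 0.978 / 0.939.

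**The case against.** The strongest reply is that the plan already handles clustering. Item 3 follows the chi-square with a patient random-effects model on the same binary split, and the natural sense of the conjunction in item 4 is that both analyses count. On that reading the simulation shows no inflation: requiring both gives the same rate as the model alone to within 0.002. One clause saying so would close the gap in item 4.

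Much of this stands. The inflated figures apply only if the chi-square alone can carry the result. But item 4 does not say that both must be significant, and item 7 has no such conjunction, so it does not protect the stopping rule. Nor can item 3 simply be taken over as the decisive test, because it leaves the covariates open and adds a normal error to a model for a binary response.

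Item 2 also does not state the unit of its chi-square. Pooling attacks follows from the definition of 1a(1). Separate tests by attack number would avoid clustering but leave up to three tests with no rule for combining them.

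Finally, the reported p-values (below 0.28, 0.24 and 0.008) are not plain chi-squares on the reported counts. Clustering or covariate adjustment could explain this, and the documents do not say which. It suggests that an unadjusted chi-square did not decide the reported result, but it does not repair the plan.

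**Conclusion.** The concern holds and should be fixed. The certain part is textual: an analysis that ignores clustering shares in the principal result with no rule of precedence, and the interim efficacy rule names no test. If the chi-square alone can suffice, true alpha with three attacks each is about 0.07, 0.12 and 0.17 at ICC 0.1, 0.3 and 0.5. At 2.15 attacks per subject it is about 0.06, 0.09 and 0.12 with equal counts, or 0.07, 0.10 and 0.13 with one to three attacks. The two tests part company, with only the chi-square significant, in 2%, 7% and 11% of null trials at three attacks, and in 1%, 5% and 8% with one to three.

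The direction is firm but the size is not. It rests on the assumed ICC, on the assumed spread of attack counts, and on every randomised subject contributing an analysed attack, with the same spread in both arms. The sizing itself is not undercut: 360 attacks carry the information of 300 (ICC 0.1) down to 180 (ICC 0.5) independent ones, always more than 120.

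**What to change.** - **Name one confirmatory test of 1a(1).** Use a binary logistic model of attack-level response at one hour, with treatment as a fixed effect, a subject random intercept, a Bernoulli likelihood without an added normal residual, and no covariates beyond any fixed in advance.
- **Amend item 4.** Take the bivariate analyses out of the sentence that determines the principal result, and label the attack-level chi-square descriptive.
- **Amend item 7.** Use the same clustered test for any interim efficacy comparison.

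Stating that both tests must be significant would also hold alpha near 0.05. A single named test is simpler, and the chi-square adds no error control to it.

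The cost is wording in the SAP, with the same data and software. P-values will be somewhat larger. Against the chi-square, power at an odds ratio of 3.2 with one to three attacks falls from 0.97, 0.96 and 0.94 to 0.96, 0.93 and 0.89 at ICC 0.1, 0.3 and 0.5, which is still above the planned 80%.
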